Other than viral vaccines for cancers of known viral origin, vaccines for prevention of cancer have not received sufficient attention. Yet, there are many non-viral antigens that are differentially expressed between normal and cancer cells, such as MUC1, that are perceived by the immune system as foreign and to which immune responses can be safely generated through vaccination. In preclinical animal models of human cancer, these vaccine-elicited immune responses have prevented cancer development or cancer progression. These studies have served as the basis for the first clinical feasibility study of the MUC1 peptide vaccine in individuals with the history of advanced adenoma who are considered at increased risk for developing colon cancer³⁴. This study showed that the vaccine consisting of 100mcg of the synthetic 100mer MUC1 peptide admixed with the TLR-3 agonist Hiltonol as adjuvant, induced anti-MUC1 IgG and long term immune memory thus confirming its immunogenicity. The study also showed that individuals with above normal numbers of circulating myeloid derived suppressor cells (MDSC) were prevented from responding to the vaccine. The randomized placebo-controlled trial described in this protocol will confirm the vaccine immunogenicity and its dependence on the MDSC and compare adenoma recurrence in vaccine responders vs. non-responders.

Colorectal Adenomas

MUC1 is overexpressed and hypoglycosylated on premalignant lesions such as adenomatous polyps, and its expression is significantly greater with higher degrees of dysplasia⁷. MUC1 is functionally important in the maintenance of the malignant phenotype. Thus, induction of an immune response against MUC1 in the setting of pre-malignancy, such as in patients with adenomatous polyps, may protect from polyp recurrence as well as from progression to cancer.

[figure not shown]

Figure1: Abnormal MUC1 is overexpressed and hypoglycosylated. Hypoglycosylated MUC1 exposes the disaccharide T antigen and the shorter monosaccharide Tn antigen attached to the protein backbone of MUC1 molecules.

Mouse model of MUC1 vaccine for colon cancer prevention

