2.4 Studies Planned in the Proposed Trial

Evaluation of anti-MUC1 antibody titer and MUC1 expression in adenomas in relation to adenoma recurrence

Anti-MUC1 IgG will be measured at w12 and w55 to measure the immune response to the vaccine in comparison to placebo, and at the time of the endpoint surveillance colonoscopy to examine the relationship between antibody titer and adenoma recurrence. In addition, sections of the qualifying advanced adenoma and of any recurrent adenomas will be obtained. Comparison of tumor associated

MUC1 antigen expression on the recurrent adenomas in relation to antibody response, and comparison among vaccine responders, non-responders, and the control group are planned.

Evaluation of anti-MUC1 antibody responses and pre-vaccination levels of circulating MDSC

Heparinized blood will be collected at week 0, 2, 10, and 12 and live PBMCs stored in DMSO and LN2 at -70 to -80°C. We plan measurements of levels of circulating MDSC in all participants. We know from the feasibility study that higher levels of MDSC were associated with lack of generation of vaccine induced antibodies. We will confirm this observation in a larger number of individuals and will evaluate MDSC levels as a variable influencing adenoma recurrence. In the placebo group, we expect to have MDSC low and MDSC high individuals in whom we can determine if adenoma recurrence rates might correlate with MDSC.

Using samples stored in the biorepository, eventually, stored PBMCs will be used to evaluate MUC1 specific T helper and CTL responses. These studies are more time intensive and expensive and funding for them will have to be obtained through other sources or other NCI grants. We do not anticipate difficulty obtaining funding for sophisticated immune assessments on this unique collection of clinical samples among participants undergoing a randomized trial of immunotherapy in a prevention setting. Within this trial, we are using T dependent antibody responses and T dependent memory responses as a surrogate marker of vaccine elicited T cells.

Placebo Response

There are several important reasons to include a placebo group. We do not know the frequency of spontaneous acquisition of antibodies to MUC1, nor do we have data on the natural history of fluctuation in antibody level over time. A control group with which to compare the antibody response and a control group with which to compare adenoma recurrence is essential.

Exclusion of Individuals with Cancer

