13.2 Randomization/Stratification

Participants will be randomized in a 1:1 fashion to one of two arms (MUC1 vs. placebo), using a dynamic allocation procedure called the Pocock-Simon⁴², which balances the marginal distributions of the stratifications factors across the intervention groups and has been shown to be able to accommodate a large number of factors (10-20) without difficulty⁴³. For this study we will use the following stratification factors: number of adenomous polyps removed ≥ 3 vs. < 3 and gender.

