13.5 Secondary Objectives, Endpoints, Analysis Plans

As discussed previously, there will be key powered secondary endpoints for this study across all 3 parts.

1) Immune response at 12 weeks (Part 1): The key secondary endpoint for Part 1 will compare the proportion of patients that have at least a 2-fold increase in the IgG ratio (week 12/week 0) between MUC1 and placebo. Based on the pilot study³⁷, we hypothesize that around 40% of vaccinated participants will demonstrate a 2 fold increase in MUC1 titer at week 12 compared to around 10% for the placebo arm. Assuming a drop-out rate of up to 10% by 1 year (presumably less by 12 weeks), retaining at least 50 evaluable participants per arm provides 94% power to detect an increase in the 12-week immune response rate from 10 to 40%, assuming a 2-sided significance level of 0.05 (nQuery Advisor 6.01).

2) Booster Response at 1 year (Part 2): The key secondary endpoint for Part 2 will assess the booster response at week 55 vs. week 52 for the vaccine as compared to placebo. Based on the pilot study, we expect 75% of week-12 responders will respond with a doubling of MUC1 antibody levels, or about 35% of the overall sample. We expect the 1-year response rate to be around 10% in the placebo group. Of the 110 randomized participants (55/arm), we expect that up to 10% will drop out by 1 year, leaving

approximately 100 participants evaluable for this analysis (50/arm). With 50 evaluable participants per arm, we would have 92% power to detect an increase in the 1-year immune response rate from 10 to 35%, assuming a 1-sided significance level of 0.05 (nQuery Advisor 6.01). We will also compare the actual IgG ratio values between the 2 treatment arms as well. If the booster vaccine shows a significant increase in the 1-year immune response as compared to placebo and a response rate that exceeds 15%, we can proceed to Part III.

3) Adenoma recurrence rate at 3 years (Part 3): Part 3 will evaluate the adenoma recurrence rate at least one year and up to 3 years. The adenoma recurrence rate at 3 years in participants with an adenoma is generally around 40-50%³³. Assuming an additional 10% drop out rate between years 1 and 3, we will have 90 participants (45/arm) evaluable for this endpoint, which will provide >80% power for the different effect sizes shown in the table below (1-sided alpha = 0.05).

# Evaluable	Effect Size (delta)	Power	1-sided alpha
90 (45/arm)	50 vs. 25%	79%	0.05
90 (45/arm)	45 vs. 20%	82%	0.05

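### Part III's claim of more than 80% power rests on unsourced whole-arm recurrence reductions of 50–62.5% that are not reconciled with the plan's 40% responder rate; if only responders benefit, power is at most about 49–62%.

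*Combined protocol and SAP*

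**What the plan says.** Part III compares adenoma recurrence between the arms. Section 13.5 item 3 gives the background rate: "The adenoma recurrence rate at 3 years in participants with an adenoma is generally around 40-50" percent. After the further loss ("Assuming an additional 10% drop out rate between years 1 and 3"), it says "we will have 90 participants (45/arm) evaluable for this endpoint". It then claims power: "which will provide >80% power for the different effect sizes shown in the table below (1-sided alpha = 0.05". The table below that sentence has three rows, each with an absolute difference of 25 percentage points:

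- 50 vs 25%: power 79%
- 45 vs 20%: power 82%
- 40 vs 15%: power 85%

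No reference or reasoning is given for the 25-point difference.

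Item 1 of the same section sets out the expected immune response: "we hypothesize that around 40% of vaccinated participants will demonstrate a 2 fold increase in MUC1 titer at week 12". The pilot figure in Section 2.3 is 17 of 39 (44%). Section 2.4 describes the role of the antibody data: "we are using T dependent antibody responses and T dependent memory responses as a surrogate marker of vaccine elicited T cells". Section 2, under Vaccines for Prevention, reports that pilot participants with raised MDSC "were prevented from responding to the vaccine", and plans a comparison of recurrence between responders and non-responders.

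**The concern.** The plan expects a minority of the vaccine arm to respond, yet it powers the clinical endpoint on a halving or more of recurrence across the whole arm. These two expectations stand a few lines apart and are never connected. If protection comes mainly through the measured response, the arm-level effect is diluted by everyone who does not respond, and the power falls well below the printed values.

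Part III is the trial's only clinical endpoint, and Sections 8.2 and 13.1 list it among the key powered endpoints. A reader who takes the claim of more than 80% power at face value could read a non-significant Part III result as evidence against the vaccine, when the trial may have had little chance of detecting benefit limited to responders.

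**Working it through.** **Inputs.** 45 per arm, one-sided alpha 0.05 and placebo rates of 50%, 45% and 40% (13.5 item 3); 1:1 allocation (13.2: "Participants will be randomized in a 1:1 fashion to one of two arms (MUC1 vs. placebo"); responder share r = 0.40 (13.5 item 1). For a wider definition of response, Section 2.3 reports 17 participants above two-fold and 4 more with ratios of 1.4–2.0, so r = 21/39 = 0.54. The protection in responders, e, is not given in the documents. I assume 50% to 100%.

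**Step 1: reproduce the printed power.** Two proportions, pooled variance under the null, no continuity correction, n = 45:

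power = Φ{[(p0 − p1) − 1.645 × √(2p̄(1 − p̄)/n)] / √([p0(1 − p0) + p1(1 − p1)]/n)}, with p̄ = (p0 + p1)/2.

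- 50 vs 25%: (0.25 − 1.645 × 0.1021)/0.0986 = 0.83, power 79.8% (printed 79%)
- 45 vs 20%: (0.25 − 1.645 × 0.0987)/0.0952 = 0.92, power 82.1% (printed 82%)
- 40 vs 15%: (0.25 − 1.645 × 0.0941)/0.0904 = 1.05, power 85.4% (printed 85%)

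The table is correct for its inputs. The first row is below 80% on either figure, so the sentence above the table does not match it.

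**Step 2: relative reductions.** 1 − 25/50 = 50%; 1 − 20/45 = 55.6%; 1 − 15/40 = 62.5%.

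**Step 3: dilution, if only responders benefit.** Vaccine-arm rate p1 = p0 × (1 − r × e). With r = 0.40 and e = 100%: 0.50 × 0.60 = 30%, 0.45 × 0.60 = 27%, 0.40 × 0.60 = 24%. The largest relative reduction is then 40%.

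**Step 4: power at the diluted rates, same formula.**

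| Responder share r | Protection e | p0 = 50% | p0 = 45% | p0 = 40% |
|---|---|---|---|---|
| 0.40 | 100% | 61.7% | 55.4% | 49.3% |
| 0.40 | 75% | 41.8% | 37.1% | 32.7% |
| 0.40 | 50% | 24.4% | 21.8% | 19.6% |
| 0.54 (21/39) | 100% | 85.3% | 79.7% | 73.2% |
| 0.54 (21/39) | 75% | 62.5% | 56.2% | 50.0% |
| 0.54 (21/39) | 50% | 36.0% | 31.9% | 28.3% |

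**Step 5: what the printed rows would need.** With benefit in responders only, e = (1 − p1/p0)/r.

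- r = 0.40: 0.500/0.40 = 125%, 0.556/0.40 = 139%, 0.625/0.40 = 156%.
- r = 21/39: 93%, 103%, 116%, so the first row becomes attainable.

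If the 40% are fully protected and the other 60% may also benefit, recurrence in those others must fall to 25/0.60 = 41.7%, 20/0.60 = 33.3% and 15/0.60 = 25.0%. These are reductions of 16.7%, 25.9% and 37.5% from the placebo rates.

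**The case against.** A reader might infer that the printed effects are impossible, so that the stated power cannot be had. The documents do not support that. It requires no benefit in anyone below the two-fold cut-off, and the plan makes no such assumption:

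- Section 3.3 says that smaller titer rises may also be clinically effective and that no titer ratio is yet known to relate to a clinical endpoint. The cut-off came partly from infectious disease practice.
- Section 2.4 treats antibody as a surrogate for T-cell responses that this trial is not funded to measure. A surrogate is not the only route to protection, and Section 2 also describes direct killing by cytotoxic T cells.
- The comparator is saline, so the contrast between arms includes the poly-ICLC adjuvant, to which Section 2 attributes immune and antiproliferative effects of its own. The documents neither quantify nor exclude an effect of it on recurrence.
- Under the wider response definition with perfect protection, the first-row placebo rate gives about 85% power, above the printed 79%.

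All of this stands. It makes the dilution figures conditional. It does not supply a basis for the 25-point differences or connect them to the expected response rate.

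A reader might also infer a calculation error, or conclude that Part III should lose its key powered label and its existing rows. The table reproduces, so there is no such error. Dropping the label or the rows is a preference: the rows are legitimate as whole-arm scenarios. Part III is also secondary, and the primary analysis and both decisions to proceed (13.4, 13.9) are immunologic and do not use this table.

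**Conclusion.** The concern holds as a conditional statement about an unsupported effect assumption. Two things are firm. The claim of more than 80% power is contradicted by the table's own 79% row. And the whole-arm reductions of 50–62.5% have no stated source and are not reconciled with the expected 40% responder rate.

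The size depends on who benefits. If only two-fold responders do, at the planned 40% share, power is at most about 62%, 55% and 49% for placebo rates of 50%, 45% and 40%, and about 24%, 22% and 20% if responders are half protected. With a 54% share and perfect protection it is about 85%, 80% and 73%. The levels of protection are assumptions, as is the absence of benefit in everyone else. The printed figures remain correct for the whole-arm effects they name.

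**What to change.** In Section 13.5 item 3:

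1. Replace the claim of more than 80% power with a statement of 79–85% power for the whole-arm effects shown, and keep the three rows.
2. Add rows using p0 × (1 − r × e) for r from 0.40 to 0.54 and e from 50% to 100%, labelled as conditional on benefit in responders only.
3. State that Part III will be reported with its estimate and confidence interval, and that a non-significant result does not exclude benefit in responders.

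This is a change of protocol wording only. The cost is that the stated power looks less favourable. No more patients are needed, and the design and the decisions to proceed are unchanged.

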13.6 Reporting and Exclusions

All randomized participants who are evaluated at week 0 and week 12 and have IgG values from those time points will be evaluable for the primary endpoint of this study using the intent-to-treat principle. We plan to over randomize assuming 10% drop out within 1 year to ensure an adequate sample size in the primary analysis cohort. There will be no imputation for missing data. A summary and listing of all major protocol violations will be provided. All details will be given in the final study report and/or manuscript. Participants lost to follow-up will be censored on the last date of assessment (or contact) and as appropriate for analyses that are dependent upon length of study participation.

13.7 Evaluation of Toxicity (secondary endpoint)

All participants will be evaluable for adverse events (AEs) from the time of their first dose of MUC1 or Placebo during parts 1 and 2 of the study. To evaluate the AE profiles associated with each arm, the maximum grade for each type of adverse event will be recorded for each participant and frequency tables will be reviewed to determine the overall patterns. The number and severity of adverse events

(overall and by arm) will be tabulated and summarized across all grades. Grade 3+ adverse events will be similarly described and summarized separately. As per NCI CTC Version 4.0, toxicities are defined as adverse events that are classified as either possibly, probably, or definitely related to the interventional agent. Overall toxicity incidence, as well as toxicity profiles will be explored and summarized within and across the MUC1 and placebo arms. Frequency distributions, graphical techniques, and other descriptive measures will form the basis of these analyses. In addition, we will review all adverse event data that are graded as 3, 4, or 5 and classified as either "unrelated or unlikely to be related" to the study intervention in the event of an actual relationship developing.

In addition, we will assess patient reported vaccine-related side effects from the Vaccine Report Card as an exploratory analysis. We will summarize the results descriptively and compare the results between the 2 arms.

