1.2 Secondary Objectives

Secondary objectives which correlate with the planned parts of the study include:

- To evaluate the ability of the vaccine to elicit a long-term memory response. We will administer a booster injection of the vaccine or placebo at week 53. Anti-MUC1 antibody response will be assessed at week 55 and compared to the week 52 pre-booster vaccine level (T55/T52). (Part II key secondary endpoint).
- To compare the adenoma recurrence rate from surveillance exams occurring at least 1 year and up to 3 years after Week 0 vaccine administration – MUC1 versus placebo (Part III key secondary endpoint).
- To compare the adenoma recurrence rates between MUC1 and placebo by excluding the following types of adenomas. These adenomas are excluded since they may represent missed or residual adenomas from the baseline exam. These analyses are exploratory.
 - Participants with adenomas ≤ 5 mm,
 - Participants with adenomatous tissue which may represent residual adenoma at the site of the previous advanced adenoma,
 - Participants with adenomatous tissue detected in the same segment of the bowel as the previous advanced adenoma.
- To assess adverse events to the MUC1 peptide vaccine in comparison to placebo during Parts I and II.
- To assess patient reported injection site reaction events from the Vaccine Report Card.

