6.2 Reported Adverse Events and Potential Risks

The side effects listed in the table below are based on a variety of previous studies that were similar to this study in some ways but different in important ways (including stronger doses) that may have led to different side effects. In the previous study that was most similar to this study, no autoimmune disease or serious side effects were identified.

Possible Side Effects of the MUC1 – poly-ICLC vaccine:

Common, Some May Be Serious In 100 people who receive the injection, more than 20 may have:

• Redness at injection site (erythema)• Pain/soreness at injection site• Flu-like symptoms, which may include fever chills, headache, fatigue, muscle pain, and joint pain• Night sweats• Loss of appetite• Low albumin blood test result (a type of protein in the blood)

The redness and soreness generally resolve within a few days to a week. Generally, acetaminophen (Tylenol®) is sufficient for pain relief. The flu-like symptoms generally resolve within 12-24 hours. Acetaminophen (Tylenol®) generally helps with these symptoms if they occur.

Occasional, Some May Be Serious In 100 people who receive the injection, 4 to 20 may have:

• Low white blood cell count (cells that fight infections)• Low platelet count (cells that help the blood clot in order to stop bleeding)• Anemia (which may cause tiredness, or may require blood transfusion)• Abnormal liver function test results

Rare, Some May Be Serious In 100 people who receive the injection, 3 or fewer may have:

• Hives, shortness of breath, or an allergic reaction that is life-threatening• Immune reaction to his or her own tissue (autoimmune diseases) or if present, may be made worse.

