11.1.3.2 Injection Site Reactions

Injection site reactions, a subset of all AEs, will also be reported by use of a participant-completed Vaccine Report Card, captured on a separate CRF, and reported to NCI, DCP. This report will not be part of the MDS. The following guidelines will be used to evaluate the injection site reaction:

Local Reaction to Injectable Product	Mild (Grade 1)	Moderate (Grade 2)	Severe (Grade 3)	Potentially Life Threatening (Grade 4)
Pain	Does not interfere with activity	Repeated use of non-narcotic pain reliever > 24 hours or interferes with activity	Any use of narcotic pain reliever or prevents daily activity	Emergency room (ER) visit or hospitalization
Tenderness	Mild discomfort to touch	Discomfort with movement	Significant discomfort at rest	ER visit or hospitalization
Erythema/Redness*	2.5 - 5 cm	5.1 - 10 cm	> 10 cm	Necrosis or exfoliative dermatitis
Induration/Swelling**	2.5 - 5 cm and does not interfere with activity	5.1 - 10 cm or interferes with activity	> 10 cm or prevents daily activity	Necrosis

* In addition to grading the measured local reaction at the greatest single diameter, the measurement should be recorded as a continuous variable.

** Induration/Swelling should be evaluated and graded using the functional scale as well as the actual measurement.

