13. STATISTICAL CONSIDERATIONS

13.1 Study Design/Description

This is a randomized Phase II double blind placebo controlled trial designed to assess the effects of the MUC1-1 peptide with poly-ILC adjuvant vs. placebo. There will be 3 "Parts" to the study to allow periodic monitoring and the opportunity to evaluate whether to proceed after each part. The key endpoints from each part are listed below:

Part I: The ratio of the week 12 to week 0 IgG levels will be calculated and compared between the MUC1 vaccine and placebo (primary endpoint, see 13.4).

Part II: Assessment of the booster response at week 55 vs. week 52 (T55/T52) for the vaccine as compared to placebo (key secondary endpoint, see 13.5)

Part III: Comparison of the adenoma recurrence rate from surveillance exams occurring at least one year and up to three years after Week 0 vaccine administration – MUC1 peptide versus placebo. All patients will be followed for this endpoint (key secondary endpoint, see 13.5)

In addition to these key powered endpoints for the 3 different parts, we will also assess the following additional secondary endpoints:

- Comparison of adverse events between the MUC1 vaccine and placebo during part 1 and 2 (13.7).
- To assess patient –reported vaccine-related side effects from the Vaccine Report Card.
- Comparison of the proportion of patients with at least a 2-fold increase in the IgG ratio between the 2 arms at 12 weeks (13.5).
- Comparison of the adenoma recurrence rates between MUC1 and placebo by excluding the following types of adenomas. These adenomas are excluded since they may represent missed or residual adenomas from the baseline exam. These analyses are exploratory.
 - Participants with adenomas ≤ 5 mm,
 - Participants with adenomatous tissue which may represent residual adenoma at the site of the previous advanced adenoma,
 - Participants with adenomatous tissue detected in the same segment of the bowel as the previous advanced adenoma.
- Assessment of participant-reported injection site reaction events from the Vaccine Report Card (Appendix E).

In addition, we will assess the following translational endpoints (see 13.10):

- To compare the anti-MUC1 antibody titer at the time of surveillance colonoscopy for the purpose of evaluating the anti-MUC1 antibody response in relation to adenoma recurrence. Since surveillance colonoscopy is generally at 3 years after an advanced adenoma, this titer will typically be obtained at approximately week 156.

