90 (45/arm)	40 vs. 15%	85%	0.05

4) As an exploratory analysis, we will also evaluate the adenoma recurrence rate from surveillance exams occurring at least 1 year and up to 3 years after Week 0 vaccine administration between MUC1 and placebo by excluding adenomas ≤ 5 mm, adenomatous tissue that may represent residual adenoma at the site of a previous adenoma, and adenomatous tissue detected in the same segment of the bowel as the previous advanced adenoma. These adenomas are excluded since they may represent missed or residual adenomas from the baseline exam. These analyses are exploratory.

5) Participant-reported injection site reaction information will be collected by use of a participant-completed Vaccine Report Card (Appendix E). Descriptive statistics will be used to summarize these data and compare the data between study arms.

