APPENDIX E

Vaccine Report Card

Dear Study Participant,

Thank you for your willingness to participate in this clinical trial of the MUC1 vaccine. This is one of the first cancer prevention vaccine trials, and we want to carefully document the vaccine experience.

In this booklet you will find a “vaccine report card” to record symptoms. Please review these instructions carefully. If you have any questions about the report card, ask your study team.

When to record symptoms:

The day of your first vaccine injection will be considered Day 0.

- On Day 2, please record symptoms you have experienced since you left your study visit. If you took any medications to relieve symptoms, please write them down. If the symptoms have disappeared, write down the date on the report card in the column labeled “date symptoms disappeared.” Once a symptom disappears, you do not need to continue recording anything about that symptom.
- On Day 7, write down all of the symptoms you experience from Day 3 to Day 7.
- On Day 14, write down all of the symptoms you experience from Day 8 to Day 14.
- If you are not scheduled to return for a study visit on or around Day 14, please send this booklet back to the study team by mail, fax, or email. Your study team members will provide an envelope, fax number, or email address for you.

What to record:

The pilot studies have shown us that some, but not all people receiving the vaccine will have reactions such as redness at the injection site, swelling, warmth or itching, and pain or tenderness. Not everyone experiences these symptoms. Some people will have no symptoms.

If there are any other symptoms you experience and want to document, please write them in the text box on the back page of this booklet.

About Injection Site Reactions

Measuring the size of the redness (erythema):

This picture shows redness of the skin. To measure this, use a tape measure or ruler to measure the maximum distance from one side of the red patch to the other in centimeters. It might be helpful to measure it across the red patch both from side to side and from top to bottom. Record the longest distance.

Pain and Tenderness:

You may experience pain at the injection site. There are two possible types. One is general muscle pain or achiness at the site that is present even when you're not touching the area, such as with movement or even sitting. The other type is tenderness, which is pain when you touch the injection site. Please record these separately.

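### Sections 13.1 and 13.7 plan a between-arm comparison of vaccine side effects from the Vaccine Report Card, but the card prompts only for injection-site reactions

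*Combined protocol and SAP*

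**What the plan says.** The plan describes the card in two ways.

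- **Wide scope.** Section 13.7 says "we will assess patient reported vaccine-related side effects from the Vaccine Report Card as an exploratory analysis" and adds that results will be summarized descriptively and compared between the two arms. Section 13.1 includes among the additional secondary endpoints patient-"reported vaccine-related side effects from the Vaccine Report Card". A separate bullet in the same list covers injection-site reactions from the card.
- **Narrow scope.** Section 1.2 gives the objective as "To assess patient reported injection site reaction events from the Vaccine Report Card". Sections 8.2 and 13.5 keep to the same scope. Section 11.1.3.2 says "Injection site reactions, a subset of all AEs, will also be reported by use of a participant-completed Vaccine Report Card", which makes the card a supplement to the AE form.

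On expected effects, Section 6.2 places in its most frequent band (more than 20 per 100) "Flu-like symptoms, which may include fever chills, headache, fatigue, muscle pain, and joint pain". It adds: "The flu-like symptoms generally resolve within 12-24 hours".

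The Appendix E card has rows for redness, pain without touch, tenderness, swelling or induration, itching, and warmth, with entries at 2, 7 and 14 days. For anything else it says: "If there are any other symptoms you experience and want to document, please write them in the text box".

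**The concern.** Under the wide wording, the card is meant to support an arm comparison of side effects in general. The systemic effects that the protocol itself names as common have no row on it. A participant who leaves the free-text page blank may have had no symptom, or may have had one and not written it down, and the data cannot separate the two.

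What is at stake is the description of tolerability. The AE comparison between arms is a secondary endpoint (8.2). Section 13.1 describes participants in such trials as high risk but otherwise healthy, and Section 2.4 cites lack of toxicity as the reason the vaccine could be used in healthy and younger people. Short-lived fever, aches and fatigue bear directly on that argument. No efficacy conclusion is affected.

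**Working it through.** The plan gives no figure to reproduce, because the card analysis is descriptive with no sample size or error rate. The check sets the card against the side-effect table and against the other route of data collection.

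**1. Coverage of the card.** Six of the six prompted rows concern the injection site. None of the six flu-like symptoms in 6.2 (fever, chills, headache, fatigue, muscle pain, joint pain) has a row. The instructions do ask in general terms for symptoms since the visit (day 2) and for all symptoms in each later interval (days 7 and 14). The back page takes other symptoms with start and stop dates, if the participant wishes to report them. It has no symptom list, None box or severity categories. The documents do not say how this text is coded or analyzed; Section 11.1.3.2 describes the card's separate form in terms of injection-site reactions.

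**2. What free text can estimate.** Let p be the true proportion with a symptom in an arm and r the proportion of those affected who write it in.

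- Card rate = p × r.
- Card difference between arms = p(vaccine) × r(vaccine) − p(placebo) × r(placebo).
- If r is the same in both arms, the difference shrinks to r × [p(vaccine) − p(placebo)], while the ratio of rates is unchanged.
- If r differs by arm, the contrast can be too small or too large.

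The documents give no value for r, so no size can be calculated. A prompted row with a None box separates no symptom from no answer, and so supplies the missing denominator.

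**3. The other route.** All AEs, related or not, go on the AE form (11.1.1) and are graded by CTCAE v4.0 (11.1.3.1). They are asked about at visits and calls (7.1, 7.3) and tabulated by arm across all grades (13.7). Flu-like symptoms enter that comparison. The first scheduled AE contact after each injection, from the windows in 7.1, is:

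| Injection | Next AE contact | Days after injection |
|---|---|---|
| Week 0 | Week 2 visit | 14 to 28 |
| Week 2 | Week 4 call, ±7 days | (28 ± 7) − 14 = 7 to 21, if the injection was on time |
| Week 10 | Week 12 visit | 10 to 21 |
| Week 53 | Week 55 visit | 10 to 21 |

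The range is 7 to 28 days, or 1 to 4 weeks. If the week 2 injection is given on day 28, the latest day allowed, the week 4 call (days 21 to 35) can fall from 7 days before to 7 days after it.

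**4. Recall gap.** Assume onset soon after injection and resolution in 12 to 24 hours.

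- Card, day 2: 48 − 24 = 24 hours to 48 − 12 = 36 hours after resolution, or 1 to 1.5 days.
- AE contact: 7 − 1 = 6 days to 28 − 0.5 = 27.5 days after resolution.

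The day-2 entry is thus the scheduled record closest to these symptoms, and it does not name them.

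**The case against.** The strongest answer is that the card was never meant for systemic effects. Four sections (1.2, 8.2, 11.1.3.2, 13.5) and one bullet of 13.1 limit it to injection-site reactions. On that reading, the wide phrases in 13.1 and 13.7 are loose wording that a small edit would cure. This stands as far as it goes: the passages conflict, and narrowing two phrases would remove the conflict. It would not change how brief systemic symptoms are ascertained.

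A reader might go further and infer that flu-like symptoms cannot be compared between arms at all. The documents do not support that. The AE form captures them, and 13.7 tabulates them by arm as a secondary endpoint. The card's general instructions and the concomitant-medication record, which includes over-the-counter drugs and their indication (5.4), may also help the AE interview.

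A reader might also take more than 20 per 100 as the rate expected in this trial. Section 6.2 cautions that its table draws on studies that differed in important ways, including stronger doses. Section 2 says that a flu-like syndrome occurred occasionally with low-dose poly-ICLC. Section 2.3 reports that some pilot participants had short-lived fever and muscle aches, with nothing above grade 1. The rate here is uncertain, which is itself a reason to ask about it.

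Finally, the direction of bias in the arm contrast is not established. The placebo is saline, and most pilot participants had erythema, so some participants may guess their arm and report differently. Structured rows would not remove that, but they would give a denominator.

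**Conclusion.** The point holds in a limited form. The card, as built, cannot support the wide analysis in 13.1 and 13.7 for systemic symptoms, and the protocol states the card's scope inconsistently. The between-arm comparison of flu-like symptoms rests on the AE form. It remains possible there, but depends on recall 1 to 4 weeks after injection for symptoms that last 12 to 24 hours.

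Under-ascertainment is therefore likely. This rests on the duration stated in 6.2, onset soon after injection, and contacts held within the 7.1 windows. Its size cannot be estimated from the documents, and any percentage would simply be a product of assumed inputs. Severity is low to moderate. The card analysis is exploratory and descriptive, the stopping rule in 13.7.1 uses related AEs of grade 3 or higher, and the decisions to proceed in 13.9 use antibody response.

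**What to change.** - Add rows to the Appendix E card for fever, chills, headache, fatigue, muscle pain and joint pain, each with None/Yes and a severity box, at the existing 2-, 7- and 14-day entries.
- Summarize these rows by arm in 13.7 as exploratory and descriptive, with completed entries as the denominator and missing entries shown separately.
- State one scope for the card in 1.2, 8.2, 11.1.3.2, 13.1, 13.5 and 13.7.
- State that the AE form remains the source for the secondary AE comparison, flu-like symptoms included.

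The cost is a revised card and form page, and about six more rows per card (6 × 3 = 18 more entries at most). No extra visit or procedure is needed.

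If the rows are not added, the minimum is to narrow 13.1 and 13.7 to injection-site reactions and name the AE form as the source for flu-like symptoms. That removes the contradiction but leaves the recall gap.
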